5. TREATMENT PLAN

5.1 Study Design

This study will consist of 3 cohorts (A1-A3) in the relapsed/refractory setting tested in two stages: 1) dose escalation and 2) dose expansion. If a combination meets prespecified safety and efficacy endpoints in the expansion stage, and after discussion with regulatory authorities, 2 additional cohorts (B1, B2) will open testing these combinations in the upfront setting in previously untreated FL patients.

The cohorts for this study will be as follows:

	Dose escalation	0	T T/ •1 1		DE 04510600
		Rituximab (or rituximab	Utomilumab	Avelumab	PF-04518600
		biosimilar)			
t A1a	Dose Level 1	375mg/m2 IV q7d for 4 doses (cycle 1 only)	100mg IV q28d cycle 1-6	3mg/kg IV q14d cycle 1-6	n/a
Cohort A1a	Dose Level 2	375mg/m2 IV q7d for 4 doses (cycle 1 only)	100mg IV q28d cycle 1-6	10mg/kg IV q14d cycle 1-6	n/a
	Dose Level 0	n/a	n/a	n/a	0.3mg/kg IV q14d cycle 1-6
Cohort A2a	Dose Level 1	375mg/m2 IV q7d for 4 doses (cycle 1 only)	n/a	n/a	0.3mg/kg IV q14d cycle 1-6
Co	Dose Level 2	375mg/m2 IV q7d for 4 doses (cycle 1 only)	100mg IV q28d cycle 1-6	n/a	0.3mg/kg IV q14d cycle 1-6
Cohort A3a	Dose Level 1	375mg/m2 IV q7d for 4 doses (cycle 1 only)	n/a	3mg/kg IV q14d cycle 1-6	0.3mg/kg IV q14d cycle 1-6
Cohoi	Dose Level 2	375mg/m2 IV q7d for 4 doses (cycle 1 only)	n/a	10mg/kg IV q14d cycle 1-6	0.3mg/kg IV q14d cycle 1-6

• Dose escalation stage:

- Dose Expansion Cohorts
 - Cohort A1b: Rituximab (or rituximab biosimilar), utomilumab, avelumab at the recommended phase 2 dose
 - Cohort A2b: Rituximab (or rituximab biosimilar), utomilumab, PF-04518600 at the recommended phase 2 dose
 - Cohort A3b: Rituximab (or rituximab biosimilar), avelumab, PF04516800 at the recommended phase 2 dose
- Upfront Cohorts (B1, B2) (n=up to 15)
 - Cohort B1: Rituximab (or rituximab biosimilar), utomilumab, avelumab at the recommended phase 2 dose
 - Cohort B2: Rituximab (or rituximab biosimilar), utomilumab, PF-04518600 at the recommended phase 2 dose

Enrollment will begin with the phase 1 dose escalation stage to test the safety of these combinations in relapsed/refractory FL and to determine the recommended phase 2 dose (RP2D) to use for the phase 1b dose expansion cohorts as well as for the potential upfront cohorts. The cohorts in the phase 1 dose escalation stage will follow a 3+3 dose escalation schema, such that there will be a safety pause and evaluation after the first 3 patients at any given dose level have completed 6 weeks of therapy. If there are no dose limiting toxicities (DLTs) seen, the next dose level will open. If there is 1 DLT, an additional 3 patients will be enrolled at that dose level with a safety pause and evaluation after all 3 have completed 6 weeks of treatment. If there are 2 or more DLTs at any time in a given dose level, no further testing of that dose level will open. The next dose levels will follow the same 3+3 dose escalation schema (**Schema 1**). Once a recommended phase 2 dose is determined, this dose will be used in both the dose expansion cohorts as well as in the potential upfront dosing cohorts.

Enrollment will begin with cohorts A1a, dose level 1, and A2a, dose level 0 in an alternating fashion. Each subsequent cohort will be filled sequentially beginning with cohort A1a dose level 2, followed by cohort A2a dose level 1, then A2a dose level 2, then A3a dose level 1, and finally A3a dose level 2. If a patient is not eligible for the cohort that is being filled preferentially at the time of enrollment due to prior treatment history, they may be enrolled in the next cohort for which they are eligible. Note, if a patient in cohort A2a, dose level 0, has not had a response by the midtreatment response assessment following cycle 3, they will be allowed to received rituximab 375mg/m2 q7d for 4 weeks during cycle 4 (C4D1, C4D8, C4D15, C4D22).

Dose limiting toxicities (DLTs) are defined as any grade 3 or greater toxicity unless directly, and incontrovertibly, related to progressive disease with the exception of the following:

- Grade 3 hematologic abnormalities
- Grade 4 hematologic abnormalities that recover to grade 2 or lower with supportive treatment (including transfusion, IVIg, or growth factor) within 7 days
- Non-hematologic abnormalities:
 - Transient (≤ 24 hours) Grade 3 fatigue, local reactions, or headache that resolves to Grade ≤ 1 ;
 - Grade 3-4 nausea and vomiting controlled by optimal medical therapy within 72 hours;

- Grade 3 hypertension controlled by medical therapy;
- O Grade 3 diarrhea that improves to Grade ≤2 within 72 hrs after medical management has been initiated;
- Grade 3 skin toxicity that resolves to Grade ≤1 in less than 7 days after medical management (eg, immunosuppressant treatment) has been initiated;
- Any Grade \geq 3 amylase or lipase abnormality that is not associated with symptoms or clinical manifestations of pancreatitis;
- Grade 3 endocrinopathies controlled with medical therapy;
- Tumor flare phenomenon defined as local pain, irritation, or rash localized at sites of known or suspected tumor.
- Non-hematologic Grade \geq 3 laboratory abnormality if medical intervention is required to treat the patient or the abnormality leads to hospitalization.
 - Single laboratory values out of normal range that are unlikely related to trial treatment according to the Investigator, do not have any clinical correlate, and resolve to Grade ≤1 within 7 days with adequate medical management are not to be considered DLTs;
- ALT or AST >3 x upper limit of normal (ULN) (if normal at baseline) or >3 x ULN and doubling the baseline (if > ULN at baseline) associated with bilirubin >2 x ULN

For part B (untreated disease cohorts), enrollment will open following the completion of the corresponding dose expansion cohort in part A (cohorts A1b and A2b), assuming that the corresponding cohort in part A meets its efficacy and safety criteria for success (\geq 3 complete responses and \leq 3 DLTs).

All cohorts in part B will have an early stopping rule if >2 patients at any point meet the criterion for a DLT.

Toxicity will be continuously monitored and recorded using CTCAE 4 criteria, up to 30 days following the last dose of the study treatment or until resolution of toxicity to grade 1 or baseline, whichever occurs last. Response will be assessed 4-6 weeks after the completion of therapy (either after cycle 6 of therapy for patients who complete the planned cycles of therapy, or after their last dose of treatment for patients who discontinue treatment before cycle 6) by PET and CT scans of the neck (if involved at baseline), chest, abdomen, and pelvis, as well as at 6, 12, and 18 months from the end of treatment (+/- 2 weeks) in the absence of disease recurrence or progression (PET may be omitted once patient is in CR). In addition, CT scans of the chest, abdomen, and pelvis +/- neck will be obtained 4 weeks (+/- 1 week) after the completion of cycle 3 while on therapy. If patients experience evidence of progressive disease confirmed by imaging while on treatment, they will be allowed to complete treatment if they meet the definition of an indeterminate response according to LyRIC criteria.²

Expected toxicities and potential risks for all drugs are described in Section 6 (Dosing Delays/Dose Modifications). No investigational or commercial agents or therapies other than those described below may be administered with the intent to treat the participant's malignancy.

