Grade 2 Mild to moderate new symptoms	Withhold all immunotherapy agents Pulmonary and Infectious Disease consults Monitor symptoms daily; consider hospitalization 1.0 to 2.0 mg/kg/day prednisone or equivalent Add prophylactic antibiotics for opportunistic infections Consider bronchoscopy, lung biopsy	Re-assess every 1 to 3 days If improves: When symptoms return to Grade ≤ 1, taper steroids over at least 1 month, and then resume all immunotherapy agents following steroids taper If not improving after 2 weeks or worsening: Treat as Grade 3 to 4.
Grade 3 to 4 Grade 3: Severe new symptoms; New/worsening hypoxia; Grade 4: Life-threatening	Permanently discontinue all immunotherapy agents. Hospitalize. Pulmonary and Infectious Disease consults. 1.0 to 2.0 mg/kg/day prednisone or equivalent Add prophylactic antibiotics for opportunistic infections Consider bronchoscopy, lung biopsy	If improves to Grade ≤ 1: Taper steroids over at least 1 month If not improving after 48 hours or worsening: Add additional immunosuppression (for example, infliximab, cyclophosphamide, IV immunoglobulin, or mycophenolate mofetil)
	Hepatic irAEs	
Grade of Liver Test Elevation (NCI-CTCAE v4)	Initial Management	Follow-up Management
Grade 1	Continue immunotherapy agents	Continue liver function monitoring If worsens:

Grade 1 AST or ALT > ULN to 3.0 x ULN and/or Total bilirubin > ULN to 1.5 x ULN		Treat a	as Grade 2 or 3 to 4.
Grade 2 AST or ALT > 3.0 to $\leq 5 \times ULN$ and/or total bilirubin > 1.5 to $\leq 3 \times ULN$	Withhold all immunotherapy agents Increase frequency of monitoring to every 3 days.	Resum immuno If eleva	ns to Grade ≤ 1: e routine monitoring; resume otherapy agents. tion persists > 5 to 7 days or worsens: s Grade 3 to 4.
Grade 3 to 4 AST or ALT > 5 x ULN and/or total bilirubin > 3 x ULN	Permanently discontinue all immunotherapy agents Increase frequency of monitoring to every 1 to 2 days 1.0 to 2.0 mg/kg/day prednisone or equivalent Add prophylactic antibiotics for opportunistic infections Consult gastroenterologist/ hepatologist Consider obtaining MRI/CT scan of liver and liver biopsy if clinically warranted	Taper s If does or rebo Add my daily If no re days, c	ns to Grade ≤ 1: steroids over at least 1 month not improve in > 3 to 5 days, worsens unds: vcophenolate mofetil 1 gram (g) twice sponse within an additional 3 to 5 onsider other immunosuppressants al guidelines.
	Renal irAEs l		
Grade of Creatinine Increased (NCI-CTCAE v4)	Initial Management		

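### As written, the DLT exception list excuses treated or hospitalised laboratory abnormalities and ALT/AST rises with raised bilirubin, while an untreated, isolated, treatment-related grade 3 ALT rise counts

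*Combined protocol and SAP*

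**What the plan says.** Section 5.1 opens with a base rule: "Dose limiting toxicities (DLTs) are defined as any grade 3 or greater toxicity". It excludes events clearly due to lymphoma progression, and then starts a list with the words "related to progressive disease with the exception of the following".

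The list contains ordinary exceptions, such as hypertension controlled by treatment, amylase or lipase rises without pancreatitis, and controlled endocrinopathies. The last of these is "Tumor flare phenomenon defined as local pain, irritation, or rash localized at sites of known or suspected tumor". With no new lead-in, the list continues:

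- **Item (i):** a non-hematologic grade 3 or higher "laboratory abnormality if medical intervention is required to treat the patient or the abnormality leads to hospitalization". A sub-bullet covers single laboratory values that are unlikely to be related to treatment, have no clinical correlate and resolve within 7 days; it ends "with adequate medical management are not to be considered DLTs".
- **Item (ii):** ALT or AST above 3 x ULN, with doubling of baseline "if > ULN at baseline) associated with bilirubin >2 x ULN".

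The text supplied contains no second definition of a DLT. Section 13.2 refers back to this one.

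**The concern.** Items (i) and (ii) read like things that should count, but they stand under a heading that says they do not. A grade 3 ALT rise that puts a patient in hospital, or that comes with bilirubin above 2 x ULN, is literally excused. The same rise, alone and untreated, is a DLT.

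The DLT count drives every safety decision in the trial: the 3+3 steps, the RP2D (a primary endpoint), the limit of 3 DLTs in 15 patients that opens a combination to untreated patients, and closure of a Part B cohort under "an early stopping rule if >2 patients at any point meet the criterion for a DLT". If sites or reviewers resolve the wording differently, they classify the same patient differently.

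Only patients whose sole qualifying event is such a laboratory value are affected. A separate grade 3 or higher clinical toxicity that is not itself excepted still counts.

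**Working it through.** **1. Item (ii) against the protocol's own grading.** The hepatic part of Table 2 (section 6.3) gives these boundaries, the grade 2 row beginning "Grade 2 AST or ALT > 3.0 to":

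| | Grade 2 | Grade 3 to 4 |
|---|---|---|
| ALT/AST | >3 to 5 x ULN | >5 x ULN |
| Total bilirubin | >1.5 to 3 x ULN | >3 x ULN |

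Item (ii) starts at ALT/AST >3 x ULN with bilirubin >2 x ULN. At ALT/AST 3 to 5 x ULN with bilirubin 2 to 3 x ULN, both measures are grade 2. The base rule never counts that event, so an exception for it is empty. Over that range item (ii) does something only as an added DLT criterion. Above it an exception is logically possible, but it would excuse the worse event.

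**2. Item (i) under three readings.** Take a treatment-related grade 3 ALT rise with bilirubin not above 2 x ULN, so that neither item (ii) nor the single-value carve-out applies:

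| Reading of item (i) | Untreated, isolated | Hospitalised for it |
|---|---|---|
| Literal: an exception | DLT | not a DLT |
| Inclusion: these are DLTs | DLT | DLT |
| Restriction: laboratory values count only if treated or hospitalised | not a DLT | DLT |

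The sub-bullet favours the second or third reading, because excusing a few mild values is largely redundant if the parent item is already excused. It does not decide between them. Both make the hospitalised case a DLT, contrary to the literal text.

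**3. The plan's own figures.** With p the DLT rate, escalation past a dose level is (1-p)^3 + 3p(1-p)^5, and the 15-patient rules are binomial.

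- Escalation at p = 0.40: 0.309 (section 13.2.1 states 0.31).
- Part A, P(3 or fewer of 15): 0.9444 at 10% and 0.0905 at 40% (stated 94% and 9%).
- Part B, P(2 or fewer of 15): 0.8159 at 10% and 0.0617 at 35% (stated 82% and 6%).

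These reproduce. The flaw lies in what is counted.

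**4. Where one patient changes a decision.**

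- 2/6 recorded as 1/6: dose level 2 becomes the RP2D.
- 4/15 recorded as 3/15: the Part A safety limit is met.
- 3 recorded as 2 in Part B: the cohort stays open.
- Inside the 3+3, 1/3 recorded as 0/3 also skips the extra three patients.

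**5. Illustration only.** The documents give no share of DLT patients affected. Suppose a share f of true DLT patients goes uncounted, so the counted rate is true rate x (1-f):

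| f (assumed) | Escalation, true 40% | Part A 3 or fewer of 15, true 40% | Part B 2 or fewer of 15, true 35% |
|---|---|---|---|
| 0 | 0.31 | 0.09 | 0.06 |
| 5% | 0.34 | 0.12 | 0.08 |
| 10% | 0.38 | 0.15 | 0.10 |
| 25% | 0.49 | 0.30 | 0.20 |

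For example, at f = 10% the Part A rate is 0.40 x 0.90 = 0.36 and P(3 or fewer of 15) = 0.1531. This models undercounting only. Under the restriction reading the literal text also overcounts, because it makes untreated values DLTs.

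**The case against.** **Layout.** Bullet levels are damaged in the extracted text. The tumor flare item ends in a full stop and the next bullet restarts with the non-hematologic category, which suggests a change of list level in the source. That is plausible, but restored indentation would not supply the missing statement that the later items are DLTs.

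**Literal use is unlikely.** Table 4 permanently stops all drugs for any treatment-related grade 3 or higher liver test abnormality. Section 7.4.3 makes ALT/AST rises with raised bilirubin and no other known cause reportable as Hy's Law cases. There are safety pauses, DSMC review, and regulatory discussion before Part B. These points stand and limit the risk to patients. They do not decide whether an event enters the DLT count.

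**The contrast is narrow.** A reader might infer that isolated grade 3 ALT rises count in general while worse ones are excused. The documents do not support that. Table 2 directs prednisone for immune-related grade 3 to 4 liver tests, and a rise treated that way falls under item (i) and is literally excused as well. The single-value carve-out removes some further isolated rises on any reading. The contrast holds only for untreated, treatment-related isolated rises.

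**Intent for item (i).** Under the base rule grade 3 laboratory toxicities already count, so plain inclusion would make item (i) redundant. That favours the restriction reading, and is a good reason for the sponsor to state its intent.

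**Rarity.** Section 8.1.4.4 reports, among 52 patients on PF-04518600 alone, AST rises in 21.2%, ALT rises in 15.4% and bilirubin rises in 11.5%. These are any grade and any cause, in advanced solid tumours, with no DLTs. Sections 7.1.1.2 and 8.1.2.4 put immune liver inflammation with avelumab below 1%, and section 8.1.1.4 reports no DLT with utomilumab alone or with rituximab. None of these is one of the trial's triplets, so the rate here stays open, but the affected share could well be small.

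**Conclusion.** Wrong as written. The misplacement is clear for item (ii) and probable for item (i); for item (i) either plausible intent makes a treated or hospitalised abnormality a DLT, so the literal text is wrong on both.

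The size is unknown. The table of assumed shares shows sensitivity and is not an estimate, and the net direction of error depends on the intent for item (i). An individual misclassification matters only at the switching counts listed above.

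A reader might infer that DLTs in this trial were miscounted or that an RP2D is unsafe. The documents do not show that sites applied the literal reading. The conclusion concerns the wording and rests on there being no other DLT definition in the text supplied.

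**What to change.** 1. End the exceptions after the tumor flare item, and keep the single-laboratory-value carve-out as one of them.
2. Add a new lead-in, *The following is also a DLT, regardless of grade:*, and place the ALT/AST-plus-bilirubin item under it.
3. Take item (i) out of the exceptions. State that non-hematologic grade 3 or higher laboratory abnormalities needing intervention or hospitalisation are DLTs, subject to the named exceptions (for example controlled endocrinopathy, or a lipase rise without pancreatitis).
4. Have the sponsor confirm whether other untreated, asymptomatic grade 3 or higher laboratory values count. Under the base rule they do.
5. Re-check recorded laboratory and liver events against the corrected list.

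The cost is a wording amendment, one sponsor decision and a data re-check, with no extra patients or procedures. Some recorded events may change status. If more of them count, an RP2D could fall or a cohort could close.

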5.2 Treatment Regimen

It is expected that treatment will be administered on an outpatient basis. A cycle will be 28 days and there will be a planned 6 cycles of therapy. Therapy will consist of the following, with each cohort consisting of 15 patients each:

5.2.1 Cycle 1

Cohort Ala:

- (i) Rituximab (or rituximab biosimilar) 375 mg/m²/dose intravenously per institutional standards for four weekly treatments for cycle 1 only, starting on day -6.
- (ii) Utomilumab 100mg intravenously over 1 hour on day 2.
- (iii) Avelumab 3mg/kg (dose level 1) or 10mg/kg (dose level 2) intravenously over 1 hour on day 16.

Cohort Alb and B1:

- (i) Rituximab (or rituximab biosimilar) 375 mg/m²/dose intravenously per institutional standards for four weekly treatments for cycle 1 only, starting on day -6.
- (ii) Utomilumab 100mg intravenously over 1 hour on day 2.
- (iii) Avelumab at the recommended phase 2 dose intravenously over 1 hour on day 16.

Cohort A2a, Dose Level 0:

(i) PF-04518600 0.3mg/kg intravenously over 1 hour on day 1 and day 15.

Cohort A2a, Dose Level 1:

- (i) Rituximab (or rituximab biosimilar) 375 mg/m²/dose intravenously per institutional standards for four weekly treatments for cycle 1 only, starting on day -6.
- (ii) PF-04518600 0.3mg/kg intravenously over 1 hour on day 2 and day 16.

Cohort A2a, Dose Level 2:

- (i) Rituximab (or rituximab biosimilar) 375 mg/m²/dose intravenously per institutional standards for four weekly treatments for cycle 1 only, starting on day -6.
- (ii) Utomilumab 100mg intravenously over 1 hour on day 2.
- (iii) PF-04518600 0.3mg/kg intravenously over 1 hour on day 16.

Cohort A2b and B2:

- (i) Rituximab (or rituximab biosimilar) 375 mg/m²/dose intravenously per institutional standards for four weekly treatments for cycle 1 only, starting on day -6.
- (ii) Utomilumab 100mg intravenously over 1 hour on day 2.
- (iii) PF-04518600 0.3mg/kg intravenously over 1 hour on day 16.

Cohort A3a:

(i) Rituximab (or rituximab biosimilar) 375 mg/m²/dose intravenously per institutional standards for four weekly treatments for cycle 1 only, starting on day -6.

- (ii) PF-04518600 0.3mg/kg intravenously over 1 hour on day 2 and day 15. PF-04518600 will be given first and must have completed administration at least 30 minutes (but a maximum of 28 hours) prior to rituximab (day 15)
- (iii) Avelumab 3mg/kg (dose level 1) or 10mg/kg IV (dose level 2) over 1 hour on day 16.

Cohort A3b:

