- (i) Rituximab (or rituximab biosimilar) 375 mg/m²/dose intravenously per institutional standards for four weekly treatments for cycle 1 only, starting on day -6.
- (ii) PF-04518600 0.3mg/kg intravenously over 1 hour on day 2 and day 15. PF-04518600 will be given first and must have completed administration at least 30 minutes (but a maximum of 28 hours) prior to rituximab (day 15)
- (iii) Avelumab at the recommended phase 2 dose intravenously over 1 hour on day 16.

5.2.2 Cycle 2-6

Cohort Ala:

- (i) Utomilumab 100mg intravenously over 1 hour once every 4 weeks x 5 (up to 5 additional doses) on day 1 of each cycle. Utomilumab must have completed administration at least 30 minutes (but a maximum of 28 hours) prior to avelumab.
- (ii) Avelumab 3mg/kg (dose level 1) or 10mg/kg (dose level 2) intravenously over 1 hour once every 2 weeks x 10 (up to 10 additional doses), on day 1 and day 15 of each cycle. On days when avelumab will be given in combination with utomilumab it must be given at least 30 minutes (maximum 24+/-4 hours) following the completion of utomilumab.

Cohort A1b and B1:

- (i) Utomilumab 100mg intravenously over 1 hour once every 4 weeks x 5 (up to 5 additional doses) on day 1 of each cycle. Utomilumab must have completed administration at least 30 minutes (but a maximum of 28 hours) prior to avelumab.
- (ii) Avelumab at the recommended phase 2 dose intravenously over 1 hour once every 2 weeks x 10 (up to 10 additional doses), on day 1 and day 15 of each cycle. On days when avelumab will be given in combination with utomilumab it must be given at least 30 minutes (maximum 24+/-4 hours) following the completion of utomilumab.

Cohort A2a, Dose level 0:

- (i) PF-04518600 0.3mg/kg intravenously over 1 hour on day 1 and day 15.
 - **If there is no response on midtreatment scans following cycle 3, patients may get Rituximab (or rituximab biosimilar) 375mg/m2 intravenously on day 1, 8, 15, and 22 of cycle 4, with PF-04518600 0.3mg/kg intravenously over 1 hour on day 1 and day 15 of this cycle. On days when rituximab will be given in combination with PF-04518600 it must be given at least 30 minutes (maximum 28 hours) following the completion of PF-04518600.

Cohort A2a, Dose level 1:

(i) PF-04518600 0.3mg/kg intravenously over 1 hour on day 1 and day 15.

Cohort A2a, Dose level 2:

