10.2 Required Data During Study

The following must be obtained during the study:

- Medical history, medication review, physical exam, and weight, ECOG performance status (see Appendix A)
- Toxicity assessment
- CBC with differential, blood chemistries including complete metabolic panel, phosphorus, magnesium, uric acid, LDH. These are required at each planned study visit during cycle 1 (C1D-6, C1D1, C1D2, C1D8, C1D15, C1D16) and on day 1 and day 15 of cycles 2-6. Patients do need to meet laboratory eligibility criteria on C1D-6.

- TSH, creatinine kinase, lipase, and triglycerides, as well as urine studies to include a urine dipstick for blood and protein and if positive a microscopic urinalysis and 24 hour urine collection (for protein) will be checked on day 1 of each cycle 1-6.
 - For patients assigned to cohorts A2, A3, and B2 with a previous history of anthracycline treatment and who are at high risk of cardiac failure (ie those that have New York Heart Association Class I heart failure), troponin I (troponin T is allowed if the assay utilized can be verified to have cardiac specificity) and Nterminal of the prohormone brain natriuretic peptide (Nt-proBNP) levels will be evaluated at every other cycle starting with cycle 2 and when clinically indicated. Any elevation in troponin or Nt-proBNP should be discussed with the study principal investigator prior to treatment.
- Pregnancy test at screening, C1D-6 (except for cohort A2a dose level 0), C1D2 (only for cohorts A1a, A1b, and B1), C1D15, and C2-6D1.
- Peripheral blood sample for biomarker studies before treatment on C1D-6 (for all cohorts except cohort A2a, dose level 0), C1D1, C1D2, C1D8, C1D15, C1D16, and on day 1 of C2-6 (Section 9).
- Tumor biopsy between C1D22 and C2D1.
- Tumor restaging: CT scans with PO and IV contrast of the chest, abdomen and pelvis (+/neck if involved at screening baseline) between C3D22 and C4D1. MRIs may be used for patients in whom CT scans are contraindicated.
 - Patients enrolled in cohort A2a, dose level 0, who have SD or PD on this scan have the option to remain on study and receive 4 weekly doses of rituximab during cycle 4 (days 1, 8, 15, and 22) while remaining the same dose and schedule of PF-04518600.
- Stool sample for biomarker studies between C1D22 and C2D1 using a home kit

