APPENDIX D RESPONSE CRITERIA FOR LYMPHOMA: LUGANO 2014 AND LYRIC

Criteria	Complete Response (CR)	Partial Response (PR)	Stable Disease (SD)	Progressive disease (PD)
Lugano	PET-CT, score 1, 2, or 3* with or without a residual mass on SPS† Or on CT, target nodes/nodal masses must regress to ≤ 1.5 cm in LDi, and no extralymphatic sites of disease	PET-CT Score 4 or 5 with reduced uptake compared with baseline and residual mass(es) of any size. Or On CT \geq 50% decrease in SPD of up to 6 target measurable nodes and extranodal sites; no increase in non-measured lesions; spleen if enlarged must have regressed by >50% in length beyond normal	Neither CR, PR, nor PD	PET-CT score 4 or 5 with an increase in intensity of uptake from baseline and/or new FDG-avid foci consistent with lymphoma at interim or end-of- treatment assessment.OrOn CT, an individual node/lesion must be abnormal with: LDi > 1.5 cm and Increase by \geq 50% from PPD nadir and An increase in LDi or SDi from nadir 0.5 cm for lesions \leq 2 cm 1.0 cm for lesions \geq 2 cm In the setting of splenomegaly, the splenic length must increase by \geq 50% of the extent of its prior increase beyond baseline (eg, a 15-cm spleen must increase to > 16 cm). If no prior splenomegaly, must increase by at least 2 cm from baseline New or recurrent splenomegaly. New or clear progression of preexisiting nonmeasured lesions. A new node > 1.5 cm in any axis or a new extranodal site > 1.0 cm in any axis; if < 1.0 cm in any axis, its presence must be unequivocal and must be attributable to lymphomaAnd/OrNew or recurrent involvement of the bone marrow

Criteria	Complete Response (CR)	Partial Response (PR)	Stable Disease (SD)	Progressive Disease (PD)
LYRIC	Same as Lugano	Same as Lugano	Neither CR, PR, PD, nor IR	As with Lugano with the following exceptions: Indeterminate response (IR) IR1: ≥50% increase in SPD in first 12 wks IR2: <50% increase in SPD with a. New lesion(s), or b. ≥50% increase in PPD of a lesion or set of lesions at any time during treatment IR(3): Increase in EDG untake without a concomitant
				 a. New lesion(s), or b. ≥50% increase in PPD of a lesion or set of lesion at any time during treatment IR(3): Increase in FDG uptake without a concomitar

SPD – sum of the product of the diameters; PPD – product of the perpendicular diameters; LDi – longest diameter; SDi – short diameter; 5PS – 5-point scale; IR – immune response

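### Sections 5.1 and 10.2 place the one scheduled on-treatment CT about 3 to 6 weeks apart, and the 5.1 timing is too late for the cycle-4 rituximab option that depends on it

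*Combined protocol and SAP*

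**What the plan says.** Two sections date the same scan differently. In Section 5.1, CT of the chest, abdomen and pelvis, with neck as needed, "will be obtained 4 weeks (+/- 1 week) after the completion of cycle 3 while on therapy". In Section 10.2, the restaging CT covers the same regions, with the neck "if involved at screening baseline) between C3D22 and C4D1".

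Two rules depend on that scan:

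- **Cycle-4 rituximab in cohort A2a dose level 0.** Section 5.2.2 opens the option with "If there is no response on midtreatment scans following cycle 3" and sets rituximab on days 1, 8, 15 and 22 of cycle 4. Section 5.1, Section 10.2 and the restaging footnote of that cohort's study calendar state the same option.
- **Continuing after apparent progression.** Section 5.4 lists progression as a reason to stop protocol therapy. Section 5.1 makes an exception for patients with imaging progression on treatment: "they will be allowed to complete treatment if they meet the definition of an indeterminate response according to LyRIC criteria". Appendix D gives one of the indeterminate categories a time limit: "IR1: ≥50% increase in SPD in first 12 wks". It does not say from which day the weeks are counted.

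**The concern.** A scan that decides whether a treatment starts on C4D1 has to be done by C4D1. Section 5.1 contains both the scan timing and the cycle-4 option, so it conflicts with itself as well as with Section 10.2.

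The date also affects LyRIC classification. A rise of 50% or more in SPD can count as IR1 only inside the 12-week limit. A scheduled scan after that limit removes the IR1 route for patients whose growth is first seen there. Indeterminate status bears on who completes treatment, and LyRIC response and LyRIC-based PFS are secondary endpoints. The scan date should therefore be the same for every patient, and its relation to the 12-week limit should be clear.

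**Working it through.** **Inputs**

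- Section 5.2, cycle length: "A cycle will be 28 days and there will be a planned 6 cycles of therapy".
- Section 5.2.1, rituximab-containing cohorts: rituximab is given "for four weekly treatments for cycle 1 only, starting on day -6". The calendars show doses on days -6, 1, 8 and 15. Weekly spacing from -6 to 1 means that day 0 is counted.
- Section 5.4: planned treatment duration of 25 weeks.
- Section 5.1: scan 28 days, plus or minus 7, after cycle 3 is complete.
- Section 10.2: scan from C3D22 to C4D1.
- Section 10: general tolerance of 2 days either way unless otherwise noted.

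**Formula.** Study day = (cycle - 1) × 28 + cycle day.

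**Check against the plan's own figure.** C6D28 = 5 × 28 + 28 = day 168. Day -6 through day 168 is 168 + 6 + 1 = 175 days, and 175 / 7 = 25.0 weeks, as stated.

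**The two windows**

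- Section 10.2: C3D22 = 2 × 28 + 22 = day 78. C4D1 = 3 × 28 + 1 = day 85.
- Section 5.1: cycle 3 ends on C3D28 = day 84. Earliest scan 84 + 21 = day 105 (C4D21), nominal 84 + 28 = day 112 (C4D28), latest 84 + 35 = day 119 (C5D7).
- Nearest edges: 105 - 85 = 20 days (2.9 weeks). Farthest edges: 119 - 78 = 41 days (5.9 weeks).
- Adding the 2-day tolerance takes the 10.2 window to day 87, still 105 - 87 = 18 days short of the 5.1 window.

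**Cycle-4 rituximab days.** C4D1, D8, D15 and D22 are days 85, 92, 99 and 106. Three precede the earliest 5.1 scan (day 105), and all four precede the nominal scan (day 112).

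**Other readings of when cycle 3 is complete**

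| Counted from | 5.1 window (days) | Distance from 10.2 window (days) | Rituximab days before earliest / nominal / latest scan | Weeks from C1D1 |
|---|---|---|---|---|
| C3D28 | 105-119 | 20 to 41 | 3 / 4 / 4 | 14.9-16.9 |
| C4D1 | 106-120 | 21 to 42 | 3 / 4 / 4 | 15.0-17.0 |
| Last cycle-3 dose, C3D15 | 92-106 | 7 to 28 | 1 / 2 / 3 | 13.0-15.0 |
| Start of cycle 3, C3D1 | 78-92 | overlaps | 0 / 0 / 1 | 11.0-13.0 |

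Only counting from the start of cycle 3 makes the windows overlap, and the sentence in 5.1 does not say that.

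**IR1 limit.** Elapsed weeks = (scan day - start day) / 7.

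- 5.1 window from C1D1: (105 - 1) / 7 = 14.9 to (119 - 1) / 7 = 16.9. From day -6: (105 + 6) / 7 = 15.9 to (119 + 6) / 7 = 17.9. Both are past 12 weeks.
- 10.2 window from C1D1: (78 - 1) / 7 = 11.0 to (85 - 1) / 7 = 12.0. From day -6: (78 + 6) / 7 = 12.0 to (85 + 6) / 7 = 13.0.

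The 10.2 window therefore lies within the limit if the weeks run from C1D1. Counted from day -6, only its first day does.

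**The case against.** The best reply is that this is one stray sentence. Section 11.1 says on-treatment assessment follows the study calendar. The restaging footnote of every calendar points to Sections 10.1 to 10.3, never to 5.1. The cycle-4 option itself presupposes a scan by about C4D1. On that view sites would follow 10.2 and nothing would go wrong. Much of this stands: 5.1 is the outlier, and nothing in the documents shows that sites have scanned at different times. It does not remove the conflict, because Section 5.1 is part of the treatment plan and gives its own explicit window.

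The reply also limits the consequences, rightly. A reader might infer that this is the only on-treatment imaging and that the IR1 rule is therefore dead under 5.1. The documents do not support that. Section 11.1 also calls for assessment when progression is suspected, so an earlier unscheduled scan could give IR1. Appendix D puts no 12-week limit on IR2 or IR3, and Section 5.1 asks for any indeterminate response, not IR1 in particular.

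The reach is narrow too. The rituximab option exists only in A2a dose level 0, a 3+3 level of 3 to 6 patients. Those patients may stay on with stable or progressive disease, so indeterminate status does not decide their retention. The primary efficacy endpoint is CR by Lugano, confirmed with PET/CT at end of treatment.

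Finally, Appendix D is a summary of cited criteria. The missing start day can be asserted of the appendix only, not of the source, which is not available here.

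**Conclusion.** The conflict holds. The two windows for the one scheduled on-treatment CT are 20 to 41 days apart with no overlap. Under 5.1, at least three of the four cycle-4 rituximab days in A2a dose level 0 pass before the scan meant to decide them. Counting from the last cycle-3 dose, which favours 5.1 more, still leaves one to three of the four days before the scan, so the option fails on its stated days under that reading as well.

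For LyRIC the conclusion is smaller: under 5.1 the scheduled scan cannot yield IR1, while the other routes to an indeterminate response stay open. Nor does the start-day question belong to 5.1 alone. The 10.2 window is inside or almost wholly outside the limit depending on whether C1D1 or day -6 is the origin. That ambiguity does not arise in A2a dose level 0, which has no day -6 dose.

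The day counts assume 28-day cycles given without delay. The number of patients whose LyRIC category would change cannot be estimated from the documents, and a distortion of the primary CR analysis is not shown.

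**What to change.** Reconcile Sections 5.1, 5.2.2 and 10.2 and the restaging footnote of the A2a dose level 0 calendar, so that one scan window is stated and is consistent with the cycle-4 option that depends on it. Which timing is right is a clinical decision for the sponsor.

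As a secondary change, state in Appendix D the day from which the 12 weeks for IR1 run, for cohorts with a day -6 rituximab dose and for the one without, so that it is clear whether the scheduled scan falls inside the limit.

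The cost is a wording amendment. No extra scan, visit or patient is needed.
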